5.5 Duration of Therapy

If at any time the constraints of this protocol are considered to be detrimental to the patient's health and/or the patient no longer wishes to continue protocol therapy, the protocol therapy should be discontinued and the reason(s) for discontinuation documented in the case report forms.

In the absence of treatment delays due to adverse events, treatment may continue indefinitely or until one of the following criteria applies:

- Documented and confirmed disease progression
- Death
- Adverse event(s) that, in the judgment of the investigator, may cause severe or permanent harm or which rule out continuation of study drug
- General or specific changes in the patient's condition render the patient unable to receive further treatment in the judgment of the investigator
- Suspected pregnancy
- Serious non-compliance with the study protocol
- Lost to follow-up
- Patient withdraws consent
- Investigator removes the patient from study
- The Siteman Cancer Center decides to close the study

Patients who prematurely discontinue treatment for any reason will be followed as indicated in the study calendar.

5.6 Duration of Follow-up

Patients will be followed every 3 months for 2 years or until death, whichever occurs first. Patients removed from study for unacceptable adverse events will be followed until resolution or stabilization of the adverse event.

6.0 DOSE DELAYS/DOSE MODIFICATIONS

6.1 Dose Modifications for Ramucirumab

Treatment modifications for toxicities not listed below will be made at the discretion of the PI. Treatment may be held for a maximum of 6 weeks before a patient must be removed from study treatment. Patients who discontinue ramucirumab must come off study but may continue to receive atezolizumab as standard of care.

6.1.1 Infusion-Related Reactions

Reduce the infusion rate of ramucirumab by 50% for grade 1 or 2 infusion-related reactions. Permanently discontinue ramucirumab for grade 3 or 4 infusion-related reactions.

6.1.2 Hypertension

Interrupt ramucirumab for grade 3 hypertension until controlled with medical management. Permanently discontinue ramucirumab for severe hypertension that cannot be controlled with antihypertensive therapy or any grade 4 hypertension.

6.1.3 Proteinuria

Interrupt ramucirumab for urine protein levels ≥ 2 g/24 hours. Reinitiate treatment

at a reduced dose once the urine protein level returns to < 2 g/24 hours. If the protein level ≥ 2 g/24 hours reoccurs, interrupt ramucirumab and reduce the dose again once the urine protein level returns to < 2 g/24 hours. Permanently, discontinue ramucirumab for urine protein level > 3 g/24 hours, if there is a third occurrence of > 2 g/24 hours, if the protein level does not return to < 2 g/24 hours within 2 weeks, or in the setting of nephrotic syndrome.

6.1.4 Venous and Arterial Thromboembolic Events, Gastrointestinal Perforation, Fistula, or Grade 3 or 4 Bleeding

Ramucirumab should be permanently discontinued in the event of a gastrointestinal perforation or fistula formation.

Patients with who develop grade 3 or 4 venous thromboembolism may receive anticoagulation and continue ramucirumab therapy provided that the tumor does not confer an excessive bleeding risk, in the opinion of the patient's physician.

Grade 3 or 4 arterial thromboembolic events, or any PE/DVT occurring or worsening during anticoagulant therapy, require permanent discontinuation of ramucirumab therapy. Any venous or arterial event leading to discontinuation of ramucirumab therapy will be considered serious and should be reported via the SAE mechanism.

6.1.5 Hepatic Encephalopathy or Other Serious Signs of Liver Impairment

For grade 2 liver test elevations, hold ramucirumab. Permanently discontinue ramucirumab for grade 3 or 4 liver test elevations or other signs of serious liver impairment. Signs of serious liver impairment include hepatorenal syndrome or other signs as determined by the treating physician.

6.1.6 Reversible Posterior Leukoencephalopathy Syndrome

If RPLS is diagnosed, ramucirumab must be permanently discontinued. All cases of RPLS must be reported via the SAE mechanism.

6.1.7 Other Non-Hematologic Adverse Events

If any other grade 3 non-hematologic adverse event occurs, hold the dose of ramucirumab and consult with the PI.

If any other grade 4 non-hematologic adverse event occurs, discontinue treatment with ramucirumab.

6.2 Dose Modifications for Atezolizumab

Atezolizumab dose reduction is not allowed. However, study treatment may be temporarily

suspended in patients experiencing toxicity considered to be related to study treatment for up to 60 days after the last dose if they experience toxicity that require a dose to be withheld. If atezolizumab is withheld because of toxicity for > 60 days after the last dose, then the patient will be discontinued from atezolizumab treatment and will be followed for safety and efficacy.

Recommendations for dosage modifications are provided in the table below:

Adverse Reaction	Severity (by CTCAE Grade)	Dosage Modifications
Pneumonitis	2	Withhold dose until grade 1 or resolved and corticosteroid dose \leq 10 mg/day (or equivalent)
	3 or 4	Permanently discontinue
Hepatitis	AST or ALT 3-5 x ULN or total bilirubin 1.5-3 x ULN	Withhold dose until grade 1 or resolved and corticosteroid dose \leq 10 mg/day (or equivalent)
	AST or ALT > 5 x ULN or total bilirubin > 3 x ULN	Permanently discontinue
Colitis or diarrhea	2 or 3	Withhold dose until grade 1 or resolved and corticosteroid dose \leq 10 mg/day (or equivalent)
	4	Permanently discontinue
Endocrinopathies (including but not limited to hypophysitis, adrenal insufficiency, hyperthyroidism, and type 1 diabetes mellitus)	2, 3, or 4	Withhold dose until grade 1 or resolved and clinically stable on hormone replacement therapy
Other immune-mediated adverse reactions involving a major organ	3	Withhold dose until grade 1 or resolved and corticosteroid dose \leq 10 mg/day (or equivalent)
	4	Permanently discontinue
Infections	3 or 4	Withhold dose until grade 1 or resolved
Infusion-related reactions	1 or 2	Interrupt or slow the rate of infusion
	3 or 4	Permanently discontinue
Persistent grade 2 or 3 adverse reaction (excluding endocrinopathies)	2 or 3 that does not recover to 0 or 1 within 60 days after last dose	Permanently discontinue
Inability to taper	Inability to	Permanently discontinue

corticosteroid	reduce to ≤ 10 mg/day (or equivalent) within 60 days after last dose	
Recurrent grade 3 or 4 adverse reaction	Recurrent grade 3 or 4	Permanently discontinue

Dose interruptions for reasons other than toxicity (e.g., surgical procedures) may be allowed, with PI approval. The PI will determine the acceptable length of interruption.

Patients who discontinue atezolizumab must come off study.

7.0 REGULATORY AND REPORTING REQUIREMENTS

The entities providing oversight of safety and compliance with the protocol require reporting as outlined below. Please refer to Appendix B for definitions and Appendix C for a grid of reporting timelines.

Adverse events will be tracked from start of treatment through 30 days after the last administration of study drug. All adverse events must be recorded on the toxicity tracking case report form (CRF) with the exception of:

- Baseline adverse events, which shall be recorded on the medical history CRF
- Laboratory adverse events that are not clinically significant

Refer to the data submission schedule in Section 11 for instructions on the collection of AEs in the EDC.

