5.2 Toxicity and Response Evaluations

All patients who receive any study treatment are evaluable for toxicity. Patients are evaluated from first receiving study treatment until a 30-day follow up after the conclusion of treatment or death.

All patients are evaluable for disease response unless they discontinue treatment prior to completion of Cycle 2 and have not had any disease assessment.

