5.3.2 Atezolizumab

Concomitant therapy includes any prescription medications or over the counter preparations used by a patient between the 7 days preceding the screening evaluation and the treatment discontinuation visit.

Patients who experience infusion-associated symptoms may be treated symptomatically with acetaminophen, ibuprofen, diphenhydramine, and/or cimetidine or another H2 receptor antagonist, as per standard practice (for sites outside the United States, equivalent medications may be substituted per local practice). Serious infusion associated events manifested by dyspnea, hypotension, wheezing, bronchospasm, tachycardia, reduced oxygen saturation, or respiratory distress should be managed with supportive therapies as clinically indicated (*e.g.*, supplemental oxygen and β_2 -adrenergic agonists).

Systemic corticosteroids and TNF α inhibitors may attenuate potential beneficial immunologic effects of treatment with atezolizumab but may be administered at the discretion of the treating physician. If feasible, alternatives to corticosteroids should be considered. Premedication may be administered for Cycles ≥ 2 at the discretion of the treating physician. The use of inhaled corticosteroids and mineralocorticoids (*e.g.*, fludrocortisone) for patients with orthostatic hypotension or adrenocortical insufficiency is allowed. Megestrol administered as appetite stimulant is acceptable while the patient is enrolled in the study.

Patients who use oral contraceptives, hormone-replacement therapy, prophylactic or therapeutic anticoagulation therapy (such as low-molecular-weight heparin or warfarin at a stable dose level), or other allowed maintenance therapy should continue their use. Females of reproductive potential should use highly effective means of contraception.

It is strongly recommended that:

- Traditional herbal medicines not be administered because the ingredients of many herbal medicines are not fully studied and their use may result in unanticipated drug-drug interactions that may cause, or confound assessment of, toxicity.
- The use of a RANKL inhibitor (denosumab) be discontinued during the study; this agent could potentially alter the activity and the safety of atezolizumab.

Patients are not allowed to receive immunostimulatory agents, including, but not limited to, IFN- α , IFN- γ , or IL-2, during the entire study. These agents, in combination with atezolizumab, could potentially increase the risk for autoimmune conditions.

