Patients should also not be receiving immunosuppressive medications, including, but not limited to, cyclophosphamide, azathioprine, methotrexate, and thalidomide. These agents could potentially alter the activity and the safety of atezolizumab. Systemic corticosteroids and anti-TNF α agents may attenuate potential beneficial immunologic effects of treatment with atezolizumab but may be administered at the discretion of the treating physician. If feasible, alternatives to these agents should be considered.

In addition, all patients (including those who discontinue the study early) should not receive other immunostimulatory agents for 10 weeks after the last dose of atezolizumab.

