5.4 Women of Childbearing Potential

Women of childbearing potential (defined as women with regular menses, women with amenorrhea, women with irregular cycles, women using a contraceptive method that precludes withdrawal bleeding, and women who have had a tubal ligation) are required to have a negative serum pregnancy test within 7 days prior to the first day of study treatment.

Female and male patients (along with their female partners) are required to use two forms of acceptable contraception, including one barrier method, during participation in the study and for 6 months following the last day of study treatment.

If a patient is suspected to be pregnant, both study drugs should be immediately discontinued. In addition a positive urine test must be confirmed by a serum pregnancy test. If it is confirmed that the patient is not pregnant, the patient may resume dosing.

If a female patient or female partner of a male patient becomes pregnant during therapy or within 6 months after the last day of study treatment, the investigator must be notified in order to facilitate outcome follow-up.

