8.1.3 Pharmacokinetics and Drug Metabolism

The pharmacokinetic (PK) characteristics of ramucirumab are similar for patients with gastric cancer, NSCLC, and mCRC based on a population PK analysis. The mean (% coefficient of variation [CV%]) clearance for ramucirumab was 0.015 L/hour (30%) and the mean terminal half-life was 14 days (20%).

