10.0 STUDY CALENDAR

Screening/baseline evaluations are to be conducted within 2 weeks prior to start of protocol therapy. Scans and x-rays must be done no more than 4 weeks prior to the start of the protocol therapy. Cycles are 21 days long. There is a +/- 3 day window for all assessments and procedures.

	Screening	Baseline	C1 D1	C2 D1	After Cycle 2	D1 of subsequent cycles	End of every 2 cycles	EOT	F/U ³
Informed consent	X								
H&P, ECOG PS	X			X		X		X	
CBC	X		X	X		X			
CMP	X		X	X		X			
PTT/aPTT, INR	X								
TSH ⁶	X		X						
Hepatitis B and C test	X								
Pregnancy test ¹	X								
Urinalysis	X		X	X		X			
CT scan	X						X		
Ramucirumab			X	X		X			
Atezolizumab			X	X		X			
Research blood		X		X					
Archival tumor		X ⁵							
Fresh biopsy		X ⁵			X ⁴				
Survival									X
AE assessment		X	-----						X ²

1. For women of childbearing potential only

2. For 30 days after end of treatment

3. Every 3 months for 2 years; may be done by phone.

4. When feasible, the biopsy will follow CT scan performed between Cycles 2 and 3

5. When available, archival biopsy tissue will be used for a baseline biopsy. If baseline tissue is not available, the patient will undergo a baseline biopsy prior to initiation of the trial.

6. Reflex to free T3, free T4.

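### Adverse-event capture ends at 30 days, counted from two different starting points, so a new immune-mediated event that starts later has no scheduled route into the toxicity summary

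*Combined protocol and SAP*

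**What the plan says.** Three places set the end of adverse-event capture. All give 30 days, but the starting point differs:

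- Section 7.0 counts from the last dose: "Adverse events will be tracked from start of treatment through 30 days after the last administration of study drug".
- Section 5.2 counts from the conclusion of treatment: "Patients are evaluated from first receiving study treatment until a 30-day follow up after the conclusion of treatment or death".
- Footnote 2 of the study calendar (Section 10.0) reads "For 30 days after end of treatment".

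For later follow-up, calendar footnote 3 reads "Every 3 months for 2 years; may be done by phone". The only item the calendar places there, apart from the 30-day adverse-event entry, is survival.

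Other provisions look beyond day 30. Section 5.3.2 bars immunostimulatory agents during the study because, combined with atezolizumab, they "could potentially increase the risk for autoimmune conditions". It adds that all patients, including those who stop early, "should not receive other immunostimulatory agents for 10 weeks after the last dose of atezolizumab". Section 6.2 lets treatment be suspended for toxicity for up to 60 days after the last dose. Beyond 60 days atezolizumab is discontinued and the patient enters safety and efficacy follow-up of unstated length. Section 5.6 follows patients removed for an unacceptable adverse event until that event resolves or stabilizes.

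Toxicity and tolerability is the fourth secondary objective (Section 2.2). Section 14.3 summarizes toxicity descriptively by grade.

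**The concern.** One of the two drugs is a checkpoint blocker, and Section 6.2 devotes most of its modification table to immune-mediated reactions. If such a reaction first appears after day 30, nothing scheduled in the plan would find it. A reader of the final toxicity table could take it as the full safety picture of the combination when it describes only treatment plus 30 days. An omission of this kind can only lower the reported frequency.

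Tolerability already carries weight: Section 1.6.1 cites it among the reasons to continue accrual after no responses in the first 12 patients. The differing starting points add a separate problem, because the same patient can be inside capture under one section and outside it under another.

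**Working it through.** The plan states no figure to reproduce here. The check sets the provisions side by side and compares their lengths.

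**Step 1. Does anything scheduled collect a new event after day 30?**

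| Provision | Reaches past day 30? | Collects a new immune-mediated event? |
|---|---|---|
| Sections 5.2 and 7.0, calendar footnote 2 | Not past 30 days from their own starting point | No |
| 3-monthly follow-up (Sections 5.6 and 10.0) | Yes, 2 years | Only survival is scheduled |
| Section 5.6, removal for an adverse event | Yes | No, only the event that caused removal |
| Section 6.2, hold beyond 60 days | Yes, no duration | Possibly, but for a subgroup, with no form or calendar row |
| Section 7.3, reporting to the drug supplier | No day limit | Acts on notification; worded for patients receiving study drug; schedules no enquiry |
| Section 11.1, Toxicity Form | Start given, no end | Section 11.0 refers back to Section 7.0, hence 30 days |

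For most patients the answer is no.

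**Step 2. Lengths, in days after the last dose.**

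- Section 5.3.2 precaution: 10 × 7 = 70; 70 − 30 = 40 days past capture.
- Section 6.2 hold: 60 − 30 = 30 days past capture.
- Section 6.1 hold, at most 6 weeks, start not stated. Counted from the last dose: 42 − 30 = 12 days past capture. Counted from a missed dose on day 21: 21 + 42 = 63, and 63 − 30 = 33 days.

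**Step 3. The starting point.** Take a patient last dosed on day 0, held for toxicity to day 60 and then discontinued.

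- Section 7.0: capture closes on day 30, while the patient is still on hold.
- Section 5.2 and the calendar, if treatment ends at discontinuation: 60 + 30 = day 90.
- The same two places, if treatment ends at the last dose: day 30.

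The readings differ by up to 90 − 30 = 60 days. If the patient resumes, the last administration moves forward and the gap closes, so the conflict affects only patients who never resume.

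A related ambiguity arises in Section 6.1: patients who stop ramucirumab leave the study but may continue atezolizumab as standard of care. The plan does not say whether those later doses count as study drug for the 30 days.

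**Step 4. Size.** With N = 21 (Section 14.2), one affected patient is 1/21 = 4.8 percentage points. The documents give no rate for late events. For an assumed rate p, the expected number is 21p and the chance of at least one is 1 − (1 − p)^21:

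| Assumed p | Expected number | Chance of at least one |
|---|---|---|
| 1% | 0.2 | 19% |
| 2% | 0.4 | 35% |
| 5% | 1.1 | 66% |
| 10% | 2.1 | 89% |

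**The case against.** The strongest reply is that 30 days is a stated, consistent length and the analysis is purely descriptive, in 21 patients, with no comparator or toxicity threshold. An incidence over a declared period is limited in scope rather than biased. That stands: the 30-day summary is valid for what it covers. It does not answer the starting-point conflict, or the lack of any scheduled enquiry afterwards.

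Several stronger readings are tempting but not supported.

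- A reader might infer that the plan declares a 10-week autoimmune risk period. It does not. The 10 weeks restrict other agents, the stated risk is that of the combination, and no reason is given for the length. That it signals continuing concern about atezolizumab is an inference, so the share of those 70 days covered by capture is not a measure of missed events.
- A reader might infer that pregnancy outcomes are lost. Section 5.4 says that if a pregnancy occurs during therapy or "within 6 months after the last day of study treatment, the investigator must be notified in order to facilitate outcome follow-up". Section 11.0 lists no pregnancy form, but the route exists.
- A reader might estimate the missed share from drug persistence. The 14-day half-life in Section 8.1.3 is ramucirumab's, and the documents give no onset distribution for late immune-mediated events. Any decay model would rest on invented values.
- A reader might conclude that late events are certain to go unrecorded. Section 6.2 promises safety follow-up to some patients, and the contents of the 3-monthly Follow Up Form are not shown. What can be said is that capture is not scheduled.

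**Conclusion.** The point holds as a gap in data capture. Followed as written, the plan schedules no collection of a new immune-mediated event starting more than 30 days after treatment, so the toxicity summary can omit such events. The effect on the reported rate is 4.8 percentage points for each patient affected. The number affected is unknown and may be zero; the probabilities above depend entirely on the assumed rates.

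Separately, and without any assumption about late risk, Sections 5.2, 6.1, 6.2 and 7.0 and calendar footnote 2 must be reconciled on when the 30 days begin and how they apply during a hold. Section 6.2 also needs to square its open-ended safety follow-up with its closing statement that patients who discontinue atezolizumab come off study.

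None of this touches the primary endpoint, the sample size, alpha or power. It is an inexpensive improvement to a secondary objective, and nothing here bears on dosing or on when treatment should be held or stopped.

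**What to change.** - **Sections 5.2 and 7.0, calendar footnote 2:** keep 30 days for all adverse events. Use one starting point in all three places and say how it applies to a patient on hold and to one who continues atezolizumab as standard of care.
- **Same places, add:** new immune-mediated adverse events, and serious adverse events at least possibly related to study drug, are asked about and recorded through the first scheduled 3-month follow-up contact. Use the existing Follow Up and Toxicity Forms. Record the date of any new anticancer therapy, including atezolizumab continued as standard of care, so that attribution can be judged. Three months is about 365/4 = 91 days, so if follow-up is counted from the last dose or later, the contact falls after the 70-day precaution.
- **Section 6.2:** give the safety follow-up a duration and a form, or refer to the same 3-month contact.
- **Section 14.3:** report toxicity by grade with and without events starting after day 30, which preserves the 30-day summary.

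Cost: protocol wording and one or two questions at a contact already planned, with no new visit or test. The downside is a few more events to enter, some recalled by phone and harder to attribute. At the time of Section 1.6.1, 9 patients were still to enroll and 3 of the first 12 remained on treatment, so these 9 + 3 = 12 could be covered prospectively. Others could be asked at their next scheduled contact.

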7.1 Reporting to the Human Research Protection Office (HRPO) at Washington University

Reporting will be conducted in accordance with Washington University IRB Policies.

Pre-approval of all protocol exceptions must be obtained prior to implementing the change.

7.2 Reporting to the Quality Assurance and Safety Monitoring Committee (QASMC) at Washington University

The PI (or designee) is required to notify the QASMC of any unanticipated problems involving risks to participants or others occurring at WU or any BJH or SLCH institution that have been reported to and acknowledged by HRPO. (Unanticipated problems reported to HRPO and withdrawn during the review process need not be reported to QASMC.)

QASMC must be notified within **10 days** of receipt of IRB acknowledgment via email to [contact]. Submission to QASMC must include the myIRB form and any supporting documentation sent with the form.

